#### 7.1.3 Baseline

Baseline is defined as the last available and valid assessment before or at date of start of study treatment. If an assessment is planned to be performed prior to the first dose of study drug in the protocol and the assessment is performed on the same day as the first administration of study drug and the time is unknown, it will be assumed that it was performed prior to study drug administration unless the protocol specifies it otherwise. Unscheduled assessments will be used in the determination of baseline. Data reported at the End of Treatment (EOT) visit are not eligible for baseline selection. The ECG baseline will be the average of triplicate ECG measurements obtained at pre-dose on Day 1 of the study treatment.

#### 7.1.4 Last Contact Date

Last contact date will be derived for patients not known to have died on or before the analysis cutoff date. Imputed dates will not be considered for the determination of last contact date. Only dates associated with patient visits or the actual assessment of the patient will be used in the derivation. Dates associated with a technical operation unrelated to patient status (e.g. the date a blood sample was processed) will not be used. Assessment dates after the cutoff date will not be used to derive the last contact date. Last contact date will only be derived using the latest complete date among the following:

- Study drug start and end dates with non-missing dose (doses of 0 are allowed)
- RECIST assessment date with evaluation marked as done
- Laboratory/PK collection date with sample collection marked as done
- Vital sign, ECG, physical exam, dermatologic exam and ophthalmic exam assessment date with non-missing parameter value
- Performance status date with non-missing performance status
- Start/end date of adverse events with non-missing verbatim term

- Start/end date of anticancer therapies administered after study treatment; discontinuation with non-missing medication/procedure term
- Date of contact for most recent post-treatment survival assessment with the status as “Alive”
- Cardiac imaging assessment date

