8.6 Monitoring for Survival Status

After patients have completed all other follow-up visits (i.e., 30-day safety follow-up visit or follow-up visits for disease progression), they will be contacted via telephone or electronic means every 3 months (Q3M; \pm 2 weeks) for survival status for 1 year after the date of the last patient's first visit. During this follow-up period, any subsequent anticancer therapies should be recorded in the eCRF.

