8.7 Collection of Data for Ongoing Patients Following Database Lock

If the primary objective of the study has been met or the Sponsor decides to stop the study early, the database may be locked for the purpose of analyzing and reporting data. Patients may continue to receive study treatment per protocol beyond database lock if the Investigator and the Sponsor agree that patients' best interests are served by continuing to receive study treatment. In patients who continue on study treatment, the Sponsor may decide to only follow for safety (i.e., collect only SAE information, not require any study-specific procedures, and mandate that patients be followed according to standard of care), where allowable per local laws or jurisdictions.

Table 10: Schedule of Events (Part A/Phase 1b)

Procedure or Assessment	Screening		Treatment					Follow-up			
			Cycle 1			Subsequent cycles					
			Day		Day		Day		Treatment Discontinuation (within 2 weeks)	30-day Safety (± 3 days) ^a	For Progression Q8W (± 1 week)
	(-28 to -1)	(-14 to -1)	1	8 (± 1)	15 (± 1)	1 (± 2)	15 (± 2)				
Informed consent	x										
Demographics	x										
Medical history ^b	x										
Eligibility criteria	x		x								
Prior treatments ^c	x		x								
ECOG PS		x	x ^d				x	x	x		
Physical exam, including body weight		x ^e	x ^d				x	x	x		
Vital signs ^f		x	x				x	x	x		
Pregnancy test ^g		x	x ^d				x	x	x		
Tumor biopsy/archived tumor tissue sample for PD-L1 expression ^h	x										
HBsAg, HCV RNA (qualitative)		x									
Triplicate 12-lead ECG ⁱ		x	x ^d				x ^j				
Single 12-lead ECG							x ^k	x			
Clinical chemistry		x	x ^d	x	x		x	x ^l	x	x	
Thyroid panel		x	x ^d				x		x	x	
Hematology		x	x ^d	x	x		x	x ^l	x	x	
Coagulation		x	x ^d				x		x	x	

Procedure or Assessment	Screening		Treatment				Follow-up					
			Cycle 1		Subsequent cycles							
	(-28 to -1)	(-14 to -1)	1	8 (± 1)	15 (± 1)	1 (± 2)	15 (± 2)	Treatment Discontinuation (within 2 weeks)	30-day Safety (± 3 days) ^a	For Progression Q8W (± 1 week)	For Survival Q3M (± 2 weeks)	
Urinalysis		x	x ^d				x		x	x		
CCI ██████████			█	█	█	█		█ ⁿ				
CCI ██████████			█	█	█	█		█				
Tumor assessments ^o	x						x ^p			x ^q		
PK Blood sample			x ^r		x ^s		x ^{r,s}					
Administer/dispense ARRY-382			Daily		Daily							
Administer pembrolizumab			x ^u				x ^u					
AEs			Review on ongoing basis					x	x			
Concomitant medications			Review on ongoing basis					x				
Survival status/subsequent anticancer therapies												x ^t

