#### 7.1.7 Reporting Conventions

Unless specified otherwise, durations of events (e.g., duration of treatment) will be calculated in days as (stop date – start date + 1).

The following conversion factors will be used to convert days into weeks, months or years:

1 week = 7 days, 1 month = 30.4375 days, 1 year = 365.25 days.

Demographics and physical measurements:

- Age (years):
  - (date of given informed consent - date of birth + 1) / 365.25
  - In case of only year and month given: Age (years): (year/month of given informed consent – year/month of birth)
  - In case only year of birth is given: Age (years): (year of given informed consent – year of birth)
  - The integer part of the calculated age will be used for reporting purposes.

All data collected in the database will be used for the statistical analysis. For each analysis a cutoff date will be determined. Only data with an assessment date or event start date (e.g. vital sign assessment date or start date of an adverse event) before or on the cutoff date will be included in the analysis.

All events with a start date before or on the cutoff date and an end date after the cutoff date will be considered as continuing at the cutoff date. The same rule will be applied to events starting before or on the cutoff date and not having a documented end date.

In general, missing values will be handled as follows unless otherwise specified. For continuous variables at Baseline, missing values will be excluded from calculation of summary statistics, and the number and percent of patients with missing values will be displayed. For categorical values at Baseline, the number and percent of patients with a missing value will be displayed. For missing post-Baseline values, the method for reporting missing values will depend on the summary table.

Qualitative/categorical data will be summarized by frequency counts and percentages. Percentages will be calculated using the number of patients or subgroup as the denominator. Continuous data will be summarized using appropriate descriptive statistics (e.g. mean, standard deviation, median, minimum, and maximum).

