#### **7.5.4 Overall Survival**

OS is defined as the time from the date of first dose of study drug to the date of death due to any cause. If a death has not been observed by the date of the analysis cutoff, OS will be censored at the date of last contact.

The survival distribution function for OS will be estimated using the KM method as described for DOR in Section 7.5.2. The OS rate at 2, 4, 6, 8 and 10 months will be estimated with corresponding two-sided 95% CIs.

Frequency counts and percentages of patients with an event (death) and censoring reasons will be summarized. Censoring reasons are as follows:

- Ongoing and no death
- Lost to follow-up

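### SAP 7.1.4 ignores post-cutoff proof that a patient is alive while SAP 7.1.7 can admit deaths learned after the cutoff; with an early cutoff this lowers late OS estimates by a few points

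*SAP*

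**What the plan says.** SAP 7.5.4 gives the OS rule: "If a death has not been observed by the date of the analysis cutoff, OS will be censored at the date of last contact". Protocol 11.1.2.1 censors OS in the same way.

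SAP 7.1.4 defines the last contact date. On scope: "Last contact date will be derived for patients not known to have died on or before the analysis cutoff date". It then closes two routes to a later date: "Imputed dates will not be considered for the determination of last contact date" and "Assessment dates after the cutoff date will not be used to derive the last contact date". So neither a later visit or call nor the cutoff date itself can stand in for the last contact.

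SAP 7.1.7 says "For each analysis a cutoff date will be determined" and admits data whose assessment date or event start date is not later than that cutoff. It does not say when the information must have been received.

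For patients who have finished all other follow-up, protocol 8.6 says that "they will be contacted via telephone or electronic means every 3 months", with a window of ± 2 weeks. Protocol 4.1 continues OS monitoring until 1 year after the last patient's first visit. Protocol 8.7 adds that, if the primary objective has been met or the sponsor stops early, "the database may be locked for the purpose of analyzing and reporting data".

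No section moves a patient confirmed alive after the cutoff to the cutoff date, and none requires a survival check at the cutoff. The special case in SAP 7.1.9.3, where last contact equals the cutoff, concerns only the imputation of a missing death date.

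**The concern.** Take two patients in survival follow-up whose last call before the cutoff was on the same day, both reached again after the cutoff. One is found to have died between the earlier call and the cutoff. On the event-date reading of SAP 7.1.7, that patient stays at risk until death and counts as an event. The other is alive. SAP 7.1.4 discards that news and censors the patient at the earlier call. Whether the person-time just before the cutoff is kept therefore depends on the outcome, which is informative censoring, and the Kaplan-Meier hazard in that window is overstated.

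OS is a secondary endpoint in every cohort. SAP 7.5.4 reports a curve, quartiles and rates at 2, 4, 6, 8 and 10 months. The cohorts are single-arm, so the results would be read against outside figures such as the 13.1-month median OS that protocol 2.1.4 reports for pembrolizumab alone in PD-L1-positive ovarian cancer.

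**Working it through.** The documents state no hypothesis, power or event count for OS, so there is no plan figure to reproduce. The check is how far the rule moves the Kaplan-Meier estimate.

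**Contact gap.** Calls are 3 months apart, each ± 2 weeks. The longest on-schedule gap is 3 + 28/30.4375 ≈ 3.9 months, using the month length in SAP 7.1.7. If the cutoff is *f* months after the last start, every patient has at least *f* months of potential follow-up. No survivor contacted on schedule is then censored before about *f* − 3.9 months. For *f* = 12 that is 12 − 3.9 = 8.1 months; for *f* = 6 it is 2.1 months.

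**Mechanism.** The estimate is the product of (1 − d/n) over death times. Under the SAP rule, survivors leave n early near the cutoff while d is unchanged. Every affected factor is too small, so the error is downward.

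**Simulation inputs.**
- From the documents: cohort sizes 29 (PDA) and 23 (prOVCA), 3-month calls, and 13.1 months as one value of median OS.
- Assumed: exponential OS, S(t) = 0.5^(t/median); other medians of 4 and 8 months; uniform 12-month accrual; median time on treatment 2 months; no loss to follow-up.
- 2,000 replicates for the +4 rows and the 23-patient +6 row, 3,000 for the others.

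Both columns count every death dated up to the cutoff. The comparison column censors all survivors at the cutoff, which assumes each is confirmed alive afterwards.

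| N, true median, cutoff after last start | SAP rule, OS at 8 / 10 months | Censored at cutoff | Shortfall (points) |
|---|---|---|---|
| 29, 8 mo, +4 | 47.0 / 37.9% | 49.8 / 41.9% | 2.8 / 4.0 |
| 23, 13.1 mo, +4 | 63.1 / 55.4% | 65.4 / 59.0% | 2.3 / 3.6 |
| 29, 4 mo, +6 | 23.6 / 15.9% | 24.9 / 17.7% | 1.3 / 1.8 |
| 29, 8 mo, +6 | 48.2 / 39.5% | 49.7 / 41.9% | 1.5 / 2.5 |
| 23, 13.1 mo, +6 | 64.1 / 56.6% | 65.5 / 58.9% | 1.4 / 2.3 |
| 29, 13.1 mo, +12 | 65.5 / 58.9% | 65.5 / 58.9% | 0.0 / 0.0 |

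The shortfalls in the 29-patient +6 and +12 rows come from unrounded means.

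- **Gap.** Survivors are censored on average 1.2 to 1.5 months before the cutoff (1.8 to 1.9 with calls 3.9 months apart).
- **Median.** For a true 13.1 months, the typical estimate under the SAP rule is 11.4 (N=23, +4), 11.7 (N=23, +6), 12.0 (N=29, +6) and 12.9 (N=29, +12). Censoring at the cutoff gives 13.3, 13.1, 13.2 and 13.1.
- **Truth.** S(8) = 0.5^(8/13.1) = 65.5% and S(10) = 0.5^(10/13.1) = 58.9%, so censoring at the cutoff recovers the true rates.
- **Sample size.** With N=500, median 13.1 months and +6, the shortfalls are 1.3 and 2.3 points. The effect does not shrink with N.

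**Removing the key condition.** If an off-treatment death counts only when a contact on or before the cutoff revealed it, N=29, median 8, +4 gives 49.7 / 41.4% (true 50.0 / 42.0%). N=23, median 13.1, +4 gives 65.3 / 58.9% (true 65.5 / 58.9%). The bias almost disappears.

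**The case against.** A reader might infer that SAP 7.1.4 biases OS downward whenever it is applied. The documents do not support that, for two reasons.

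First, the effect needs deaths learned after the cutoff to be added as events. SAP 7.1.4 speaks of patients not known to have died, and SAP 7.5.4 of a death not observed by the cutoff. Both can be read as requiring the death to be known by then, and neither document describes a survival sweep or a lag between cutoff and lock. On that reading there is almost no bias. This stands as a condition. It does not remove the point, because SAP 7.1.7 selects by event date and nothing excludes a late-reported death.

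Second, the planned horizon is long. SAP 1.0 concerns the final analysis, SAP 7.9 plans no formal interim analysis, and protocol 4.1 and 4.3 point to 1 year of follow-up after the last patient starts. At that cutoff the landmarks do not move, and hardly any scheduled survival calls remain after it. This also stands. But the SAP ties no cutoff to that horizon, and the Phase 2 primary endpoint, ORR, can read out earlier.

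Three smaller points are fair:
- The contact model leaves out the 8-weekly scans after discontinuation without progression (protocol 8.5), and adverse-event and subsequent-therapy dates, all of which SAP 7.1.4 accepts as contacts. The gaps therefore lean high.
- The bias lies within a sampling standard deviation of about 10 to 13 points in the 12-month-accrual, +4 runs.
- Larger shortfalls, about 5 and 9 points with 8-month accrual and a cutoff at +4, come from a 10-month landmark that only about a quarter of patients could reach (2 of 8 accrual months). They should not be quoted as typical.

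**Conclusion.** The point holds in conditional form. The text allows post-cutoff information to be used for deaths and refuses it for survivors. If pre-cutoff deaths are in fact learned after the cutoff, and the cutoff comes well before 1 year after the last start, late OS estimates are biased downward. For a cutoff 4 to 6 months after the last start, the size is about 1 to 3 points at 8 months and 2 to 4 points at 10 months, with a true median of 13.1 months typically estimated at about 11.5 to 12. These figures rest on exponential survival, 12-month accrual and the simplified contact schedule above.

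At a cutoff 12 months after the last start, rates up to 10 months are unaffected and the median barely moves. An unqualified statement that the trial's OS results will be too low would go beyond the documents. Severity is low: OS is secondary and descriptive, no hypothesis is tested on it, and no error rate, stopping rule or primary conclusion depends on it.

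**What to change.** Add to SAP 7.1.4: for OS, a patient with any contact after the cutoff showing them alive, or with a death dated after the cutoff, is censored at the cutoff date. State this as an exception to the date rule in SAP 7.1.7, so that post-cutoff information is used alike for survivors and deaths. Limiting the change to OS leaves the other uses of last contact date, such as the imputations in SAP 7.1.9, as they are.

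The cost is one sentence and one programming line, using contacts already in the database at extraction. No new visits are needed. A survival check around the cutoff would make the rule more complete, at some cost in site effort, but the fix does not depend on it.

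Two edits nearby are optional clarifications and do not bear on the bias. One is to state how last contact date is derived for patients who died, since SAP 7.1.9.3 uses it for them. The other is to add withdrawal of consent to the OS censoring reasons in SAP 7.5.4, as SAP 7.5.2 already does for duration of response.

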#### 7.1.5 Treatment Start Date

Treatment start date is defined as the date patient receives the first non-zero dose of study drug.

#### 7.1.6 Study Day

Study day is defined in the following manner:

- On or after the start date of study treatment: (date of assessment) – (treatment start date) + 1. Study day 1 will therefore be the first day of study treatment.
- Before the start date of study treatment: (date of assessment) – (treatment start date).

#### 7.1.7 Reporting Conventions

Unless specified otherwise, durations of events (e.g., duration of treatment) will be calculated in days as (stop date – start date + 1).

The following conversion factors will be used to convert days into weeks, months or years:

1 week = 7 days, 1 month = 30.4375 days, 1 year = 365.25 days.

Demographics and physical measurements:

- Age (years):
  - (date of given informed consent - date of birth + 1) / 365.25
  - In case of only year and month given: Age (years): (year/month of given informed consent – year/month of birth)
  - In case only year of birth is given: Age (years): (year of given informed consent – year of birth)
  - The integer part of the calculated age will be used for reporting purposes.

All data collected in the database will be used for the statistical analysis. For each analysis a cutoff date will be determined. Only data with an assessment date or event start date (e.g. vital sign assessment date or start date of an adverse event) before or on the cutoff date will be included in the analysis.

All events with a start date before or on the cutoff date and an end date after the cutoff date will be considered as continuing at the cutoff date. The same rule will be applied to events starting before or on the cutoff date and not having a documented end date.

In general, missing values will be handled as follows unless otherwise specified. For continuous variables at Baseline, missing values will be excluded from calculation of summary statistics, and the number and percent of patients with missing values will be displayed. For categorical values at Baseline, the number and percent of patients with a missing value will be displayed. For missing post-Baseline values, the method for reporting missing values will depend on the summary table.

Qualitative/categorical data will be summarized by frequency counts and percentages. Percentages will be calculated using the number of patients or subgroup as the denominator. Continuous data will be summarized using appropriate descriptive statistics (e.g. mean, standard deviation, median, minimum, and maximum).

For reporting conventions, minimum and maximum values will be presented with the same decimal precision as collected in the raw data; mean, median, and quartiles should generally be presented to one more decimal place than the raw data; standard deviation should be displayed to two more decimal places than the raw data. Percentages will be reported to one decimal place. Unless otherwise noted, for all percentages, the number of patients in the analysis set who have an observation will be the denominator.

All analyses will be performed and summarized for Phase 1b and Phase 2 separately. All Phase 1b tables will be presented by the following 4 groups, and the listings will be presented by the first 3 groups:

200 mg ARRY-382 + 2 mg/kg Pembro	400 mg ARRY-382 + 2 mg/kg Pembro	300 mg ARRY-382 + 2 mg/kg Pembro	All Phase 1b Patients
-------------------------------------	-------------------------------------	-------------------------------------	--------------------------

All Phase 2 tables, listings and figures will be presented by the following 3 groups:

PD-1/PD-L1 Inhibitor Refractory	prOVCA	PDA
---------------------------------	--------	-----

Data listings will be created for Phase 1b and Phase 2 separately, and will be sorted by patient identifier, parameter, and the corresponding date of assessment. The listing source will be included in the footer of the listings.

### 7.1.8      **Unscheduled Visits**

Generally, data collected at unscheduled visits will be included and analyzed for both safety and non-safety analyses in the same fashion as the data collected at scheduled visits except where otherwise noted in the sections that follow. Descriptive statistics (mean, standard deviation, median, minimum, maximum, quartiles) by nominal visit or time point for safety endpoints such as laboratory measurements, ECGs and vital signs will include data from scheduled visits only.

### 7.1.9      **Imputation Rules for Partial or Missing Dates**

#### 7.1.9.1    **Prior and Concomitant Medications**

Incomplete concomitant medication dates will be imputed as follows:

##### **Medication start date**

- If only day of the month is missing,
  - If month and year match that of the treatment start date, then impute as (treatment start date + 1).
  - If month and year fall before the study treatment start date, then impute the concomitant medication start date as the 15th day of the month.
  - If month and year fall after the treatment start date, then impute as the 1st day of the month.
- If both day and month are missing,
  - If the year matches that of the treatment start date, then impute as the start date for concomitant medication (treatment start date + 1).
  - If the year is prior to the treatment start date, then impute start of the concomitant medication as July 1st.
  - If the year is after the treatment start date, then impute as January 1st.
- In all other cases the incomplete medication start date will not be imputed.

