### 7.1.9.2 Adverse Events

The imputation of the start date and end date of AEs will follow the same conventions as for concomitant medication start date and end date.

AEs that are completely missing a start date will be considered as treatment emergent if the end date of the AE is either missing or occurs after the treatment start date. In this case, impute AE start date to be treatment start date.

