### 7.1.9.3 Death Date

Missing or partial death dates will be imputed based on the last contact date:

- If the date is completely missing, it will be imputed as the day after last contact date.
  - Note: A special case is the patient’s last contact date is the same as the data cutoff date. In this case, his death date will be imputed as the day after the last contact date. Therefore, he would be still alive as of the data cutoff date.
- If the day or both day and month are missing, death date will be imputed to the maximum of the full (non-imputed) [last contact date (excluding the date of death) + 1] and the following:
  - Missing day: 15th day of the month and year of death
  - Missing day and month: July 1st of the year of death

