#### 7.1.9.6 Dates of Anticancer Therapies

##### Prior therapies:

Incomplete start dates will be handled by applying the same imputation rules as AE/concomitant medications start date except:

- If only day is missing, and month and year match that of the treatment start date, impute as date of first dose of study drug -1;

- If both day and month are missing, and the year matches that of the treatment start date, then impute as date of first dose of study drug – 1;
- Completely missing start date is imputed as date of first dose of study drug – 1.

Incomplete end dates and dates of progression on the prior anticancer therapies will be handled using the following rule:

- If only day is missing, imputed date = min (first dose of study drug -1, last day of the month);
- If both month and day are missing, imputed date = min (first dose of study drug -1, 31DEC);
- Completely missing end dates will not be imputed.

If the end date or the date of progression is not missing, and the imputed start date is after the end date or after the date of progression, use the min (end date, date of progression) as the imputed start date.

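### SAP 7.1.9 lets a partial medication or AE start be imputed after its own known end, and a partial death date after the cutoff by which the death was known

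*SAP*

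**What the plan says.** **Medication starts (SAP 7.1.9.1).** With only the day missing: "If month and year match that of the treatment start date, then impute as (treatment start date + 1". With day and month missing and the year equal to that of first dose: "impute as the start date for concomitant medication (treatment start date + 1". Starts of non-drug therapies follow the same convention. The worked examples in Table 3 of that section have no end-date column.

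**AEs (SAP 7.1.9.2).** Start and end imputation "will follow the same conventions as for concomitant medication start date and end date". Only an AE whose start is wholly missing has its end examined: it is "considered as treatment emergent if the end date of the AE is either missing or occurs after the treatment start date".

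**Prior anticancer therapies (SAP 7.1.9.6).** A cap exists here. When the imputed start falls after a known end or progression date, the instruction is to "use the min (end date, date of progression) as the imputed start date".

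**Death (SAP 7.1.9.3).** "If the day or both day and month are missing, death date will be imputed to the maximum of the full (non-imputed" last contact date + 1 and a default, which is the 15th if the day is missing and 1 July if day and month are missing. A Note covers one cutoff case only: a completely missing date with last contact on the cutoff, where the patient is counted as alive.

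**How the dates are used.** SAP 7.6.4 defines a new TEAE by its start. SAP 7.6.2 defines concomitant use by start (or by continuation past first dose), while SAP 7.4.6 defines prior use by stop date. Under SAP 7.1.7 only data dated "before or on the cutoff date will be included in the analysis". SAP 7.5.4 censors OS at last contact if no death has been observed by the cutoff.

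**The concern.** The two rules share a weakness: each ignores a fact already in hand.

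For starts, that fact is the end date. If a drug or event stopped before first dose, its timing relative to treatment is settled whatever the start day was. The rule still places the start one day after first dose, and the tables classify on that start. A medication then appears in both the prior and the concomitant summaries, and a resolved screening event can enter the TEAE tables.

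For deaths, the fact is that the patient was known to be dead by the cutoff. The rule supplies a floor (last contact + 1) but no ceiling, so a default date can fall beyond the cutoff. The patient is then censored at last contact although known to have died, which biases OS in the favourable direction. Death is also an event for PFS, DOR and irPFS.

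**Working it through.** **Inputs.** The start, end and death rules in SAP 7.1.9.1 to 7.1.9.3; the cutoff and duration conventions in 7.1.7; TEAE, concomitant and prior definitions in 7.6.4, 7.6.2 and 7.4.6; event and censoring rules in 7.5.2 to 7.5.4; AE recording in protocol 10.5. The 2019 dates and the known end dates below are illustrative.

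**1. The SAP's own examples.** Applied literally, the rules reproduce all 7 start-date rows of Table 3 and all 8 end-date rows of Table 4 in 7.1.9.1. For instance, with first dose 20OCT2001, DDOCT2001 and DDMMM2001 both give 20OCT2001 + 1 = 21OCT2001, and DDSEP2001 gives 15SEP2001.

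**2. Add a known end date (first dose 20OCT2001).**
- DDOCT2001, ended 12OCT2001: start 21OCT2001, 9 days after the end; classified as on treatment.
- DDMMM2001, ended 05MAR2001: start 21OCT2001, 230 days after the end; classified as on treatment.
- DDSEP2001, ended 10SEP2001: start 15SEP2001, 5 days after the end. This is inconsistent, but it creates no TEAE.

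For a day-missing start in the first-dose month, the error occurs for every possible pre-dose end day: 1 to 19 October, 19 of 19.

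With start = min(imputed start, known end), these become 12OCT2001, 05MAR2001 and 10SEP2001, none of them treatment-emergent. All 7 Table 3 rows are unchanged when the end is missing or later.

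**3. Partial deaths.** Imputed death = max(last contact + 1, default). Take last contact 20FEB2019.
- DDMAR2019, cutoff 10MAR2019: max(21FEB2019, 15MAR2019) = 15MAR2019, after the cutoff, so OS is censored at 20FEB2019.
- DDMMM2019, cutoff 30APR2019: max(21FEB2019, 01JUL2019) = 01JUL2019, after the cutoff, so OS is censored at 20FEB2019.

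With min(imputed death, cutoff), applied only to deaths known to be on or before the cutoff, these become events on 10MAR2019 and 30APR2019.

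**4. When the cutoff exposes the gap.**
- A day-missing death in the cutoff month is dated late if the cutoff is on days 1 to 14: 12 × 14 = 168 of 365 dates, 46%.
- A year-only death in the cutoff year is dated late if the cutoff is before 1 July: 181 of 365 dates, 50%.
- The 15th rule cannot push a day-missing death in a month before the cutoff month past the cutoff.

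These are shares of possible cutoff dates, not of deaths.

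**5. Reach into PFS, DOR and irPFS.** SAP 7.5.3 censors a PFS event that follows more than one missing or inadequate assessment, 7.5.6 applies this to irPFS, and 7.5.2 lists the corresponding DOR censoring reason. On the 6-weekly schedule two scans are missed after about 2 × 42 = 84 days. In the second death example, 30APR2019 − 84 days = 05FEB2019. If the last adequate scan was on or before about that date, PFS is censored there with or without the cap. If it was later (up to 20FEB2019), the cap restores the event.

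**The case against.** The case on the other side is substantial.

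- **The SAP is not without bounds.** A reader might infer that its date rules have no caps at all. That is not so: 7.1.9.4 bounds the last-dose date by end of treatment and death and floors it at first dose, 7.1.9.6 caps prior-therapy starts, and 7.1.9.2 checks the end for wholly missing AE starts. The gap is specific to partial medication, non-drug and AE starts and to death dates.
- **False TEAEs will be rare.** Protocol 10.5 puts pre-dose events on the AE form only if related to a study procedure. The event must also have resolved before dosing, with an unknown start day and a known end. This stands. Medications are more exposed, because protocol 6.5.1 collects non-cancer treatments taken within 4 weeks of screening.
- **Calling uncertain starts on-treatment is deliberate caution.** Table 3 labels such rows uncertain, and 7.6.4 defaults to treatment-emergent when timing is unknown. But a known pre-dose end makes the timing known, so the policy does not cover these records.
- **No planned table reports AE or medication duration.** Negative durations would therefore not reach an output. This stands.
- **The death problem needs several conditions together.** The date must be partial and in the cutoff month or year, the cutoff must fall before the 15th or 1 July, and the death must truly be on or before the cutoff. If data are extracted later, a partial date may really lie after the cutoff and the present rule is then right. This stands, and it limits the fix to deaths known by the cutoff.
- **The documents do not show that a report date for death is collected.** This also stands; the SAP would need to name the evidence it uses.

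**Conclusion.** Both gaps follow from the SAP as written. They are stated rules that give a wrong answer in identifiable cases, and the SAP's own handling in 7.1.9.6 and of wholly missing AE starts shows the start-date gap is an omission.

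The size is small. The start-date error affects descriptive tables only: double-counted medications and perhaps an occasional false TEAE. The death-date error affects OS, and affects PFS, DOR and irPFS only where the missed-assessment rule does not already censor. One affected patient is 1/23 = 4.3% of the prOVCA cohort or 1/29 = 3.4% of the PDA cohort at full Simon enrolment. The documents give no basis for an expected number of partial dates, so neither a frequency nor a Kaplan-Meier shift can be estimated.

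A reader might infer that the safety profile or the trial's efficacy conclusion is materially distorted. The documents do not support that: pre-dose AE recording is restricted, OS is a descriptive secondary endpoint, the affected patient still contributes follow-up to last contact, and ORR does not depend on these dates.

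The conclusion assumes the rules are programmed literally and, for deaths, that the death is known to have occurred by the cutoff.

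**What to change.** - **7.1.9.1 and 7.1.9.2:** add that if the end date is known, or a partial end date shows the item ended before first dose, and it is earlier than the imputed start, the start is set to the end date. This mirrors 7.1.9.6. State that it also covers non-drug therapies. An item whose start and end both lack the day within the first-dose month stays uncertain and keeps the existing default.
- **7.1.9.3:** add that if the death is known to have occurred on or before the cutoff (for example, it was reported or entered by then), the imputed date may not be later than the cutoff. Name the data item that establishes this. Align the Note on completely missing death dates so that a death known by the cutoff is not counted as alive.

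The cost is a sentence in each of the three sections, a revised Note and a few lines of code, all before database lock. No example in Table 3 or Table 4 of 7.1.9.1 changes. The one practical need is a usable indicator that the death was known by the cutoff.
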